13.5.2 Secondary Endpoints

Overall survival (OS) for both cohorts: The analyses for OS will follow ITT principle and will be conducted separately within each cohort (pancreatic NET and carcinoid tumor).

The distribution of OS will be estimated using the method of Kaplan-Meier. The median OS, along with the 95% confidence intervals, will be estimated for the two treatment groups. Additionally, 3-year OS rate, along with the 95% confidence intervals, will be estimated for the two treatment groups.

Overall survival will be compared between treatment arms using the stratified log-rank test at a one-sided cumulative 2.3% level of significance. The stratified Cox regression will be used to estimate the hazard ratio (HR) of OS, along with the 95% confidence interval. A hierarchical approach will be used to control for family-wise type-I error rate, therefore OS will be formally statistically tested only if the primary efficacy endpoint, PFS, is statistically significantly different between the two treatment groups.

The best historical data related to OS outcome in patients with pancreatic NET and progressive disease comes from the results of the placebo arms of the RADIANT-3 study and the randomized study of sunitinib vs. placebo. In the RADIANT-3 study, median OS was 37.7 months in patients who received placebo. In the phase III study of sunitinib vs. placebo in patients with pancreatic NET, median OS was 29.1 months in patients who received placebo.

The best historical data available related to OS outcome in patients with carcinoid tumors and progressive disease comes from the results of the placebo arm of the RADIANT-2 study. In the RADIANT-2 study, median OS was 35.8 months in patients who received octreotide with placebo. The final OS analysis has not been reported for the RADIANT-4 study, which included patients with nonfunctional carcinoid tumors who were randomized to receive everolimus or placebo.

Because patients in this trial are required to have experienced disease progression on at least one line of prior systemic therapy not including somatostatin analogs, we anticipate that the median OS time in patients receiving placebo in both cohorts of this trial may be shorter than what has been reported in the clinical trials mentioned above.

The OS analyses within each cohort will be conducted when approximately 155 OS events have been observed. Based on the assumed accrual rate and target sample size specified in previous sections, the anticipated analysis times for the final OS analysis are approximately 86 months and 68 months for the pancreatic NET and carcinoid tumor cohorts, respectively.

13.5.3 Adverse Events (AEs)

AEs and the maximum grade for each type of adverse event will be recorded for each patient. Similarly, scores (0-4) and the maximum score for each PRO-CTCAE item will be recorded for each patient. For patients who elect to crossover to open-label cabozantinib at centrally-confirmed PD, only adverse events that occur prior to crossover will be considered for endpoint. Any AEs that occur after crossover for these patients will be analyzed separately in a descriptive fashion.

For CTCAE data, the frequency tables will be reviewed to determine the patterns. The overall adverse event rates will be compared between treatment groups using Chi-square test (or Fisher's exact test if the data in contingency table is sparse).

PRO-CTCAE data will, at minimum, be analyzed similarly to CTCAE data. Reasons for missed PRO-CTCAE assessments will be collected, and we will describe the extent of

missing data as well as its patterns and causes. The initial analysis of each PRO-CTCAE item will use all available scores in an analysis which mirrors the approach used for the CTCAE data. Supplemental analysis will use model-based multiple imputation incorporating baseline patient characteristics and physician-rated performance status (which is collected at each cycle). CTCAE data may be incorporated as auxiliary data into multiple imputation models for AEs which are captured by both PRO-CTCAE and CTCAE. Results from supplemental analysis will be descriptively compared to the results of the initial analysis to assess the robustness of results to missing data. Since a preferred or optimal statistical methodology for PRO-CTCAE data is yet to be determined, additional analyses of PRO-CTCAE data beyond those specified above may be undertaken based on the current state of the science at time of data maturity for this study.

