- A To be performed at baseline, on Day 1 of Cycle 2, and on Day 1 of Cycle 3.
- B Any adverse events that occur within 30 days of discontinuation of study treatment should be recorded in the last treatment cycle form.
- C To be performed at baseline, and then every 12 weeks (+/- 1 week) (i.e. every 3 cycles). Any measurements of biochemical response should occur in conjunction with the radiographic assessments for disease status.
- D To be performed every other cycle (i.e. Cycle 1, Cycle 3, Cycle 5, etc.).
- For patients with a history of carcinoid syndrome only: perform 24-hour urine 5-HIAA at baseline and then every 12 weeks (+/- 1 week) (i.e. every 3 cycles). Other hormones, such as gastrin, insulin, glucagon, and VIP should be assessed, if clinically indicated, at baseline and then every 12 weeks (+/- 1 week) if elevated. Any measurements of biochemical response should occur in conjunction with the radiographic assessments for disease status. For patients with functional neuroendocrine tumors (i.e. patients with symptoms related to hormone production) only: perform hormone assessment, if clinically indicated, at baseline and then every 12 weeks (+/- 1 week) if elevated.
- Baseline scans and scans within the 12 months prior to registration used to determine progression for eligibility should be submitted within 3 days; see Section 3.2.1, Section 6.3, and Section 7.2.3. Restaging scans will be performed after every 12 weeks (+/- 1 week) (i.e. every 3 cycles) until evidence of progression; restaging scan used for local determination of progression while on blinded therapy must be submitted for real-time central review within 24 hours; see Section 6.3 and Section 7.2.2.

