7.0 TREATMENT PLAN/INTERVENTION

7.1 Cabozantinib/Placebo

Protocol treatment is to begin \leq 14 days of registration or re-registration.

For questions regarding treatment, please see the study contacts page.

Blinded Therapy

This is a 2:1 randomized, double-blind trial. The initial blinded, patient-specific clinical supplies of cabozantinib/placebo will be requested by the Alliance Statistics and Data Management Center at the time of randomization and should arrive at the clinical site \leq approximately 7-10 days after randomization (see Section 10.1).

Protocol therapy will consist of 60 mg oral cabozantinib/placebo (three 20 mg tablets) taken once daily during each 28-day treatment cycle. Patients should not eat for at least 2 hours before and for at least 1 hour after taking cabozantinib/placebo.

Treatment will continue until disease progression, unacceptable toxicity, or withdrawal of consent. Crossover from placebo to open-label cabozantinib at the time of centrally-confirmed radiologic disease progression is permitted; see Section 3.3, Section 4.8, Section 6.3, and Section 7.2. Patients will be monitored for treatment response and toxicity.

Open-label Therapy

The open-label, patient-specific clinical supplies of cabozantinib will be requested by the Alliance Statistics and Data Management Center at the time of re-registration and should arrive at the clinical site \leq approximately 7-10 days after re-registration (see Section 10.1).

Protocol therapy will consist of 60 mg oral cabozantinib (three 20 mg tablets) taken once daily during each 28-day treatment cycle. Patients should not eat for at least 2 hours before and for at least 1 hour after taking cabozantinib.

Treatment will continue until disease progression, unacceptable toxicity, or withdrawal of consent. Patients will be monitored for treatment response and toxicity.

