13.2 Sample Size

Pancreatic NET Cohort

The best historical data available on the outcome of patients with pancreatic NET and progressive disease comes from the results of the placebo arms of the RADIANT-3 study and

the randomized study of sunitinib vs. placebo. In these studies, the progression-free survival (PFS) in patients receiving placebo was approximately 5 months.

We assume an accrual period of 2.6 years (31 months), 6 patients per month, 4.32% of dropout, minimum follow-up in all other patients of 8 months, exponential survival, and that a one-sided log-rank test for superiority will be conducted at level 0.025. We also assume PFS of 5 months for patients receiving placebo. Based on these assumptions, a sample size of 185 patients (124 in cabozantinib arm and 61 in placebo arm) will result in 149 events which are required to provide 90% power to detect a hazard ratio (HR) of 0.568 between the two treatment arms. The PFS estimate corresponding to this HR is 8.8 months.

Carcinoid Tumor Cohort

The best historical data available on the outcome of patients with carcinoid tumors and progressive disease comes from the results of the placebo arms of the RADIANT-2 and RADIANT-4 studies. In the RADIANT-2 study, the PFS according to investigator review in patients receiving placebo was 8.6 months. In the RADIANT-4 study, the PFS in patients receiving placebo was 3.9 months.

We assume an accrual period of 2.9 years (35 months), 6 patients per month, 4.286% of dropout, minimum follow-up in all other patients of 11 months, exponential survival, and that a one-sided log-rank test for superiority will be conducted at level 0.025. We also assume PFS of 7 months for patients receiving placebo. Based on these assumptions, a sample size of 210 patients (141 in cabozantinib arm and 69 in placebo arm) will result in 164 events which are required to provide 90% power to detect a hazard ratio (HR) of 0.583 between the two treatment arms. The PFS estimate for the cabozantinib corresponding to this HR is 12 months.

For Both Cohorts

The rate of PFS events and censoring will be monitored over the course of the study; if it appears that the study will not reach the requisite number of PFS events within the planned study timeframe, the protocol may be amended to increase the total sample size.

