13.3.2 Secondary Endpoints

For both cohorts: overall survival, adverse events, and radiographic response rate.

Overall Survival (OS)

The secondary endpoint of this study is overall survival, defined as the time from randomization to death, from any cause. Patients who do not have an OS event will be censored for OS at the date they were last known to be alive.

Adverse Events (AEs)

CTCAE AEs and the maximum grade for each type of AE will be recorded for each patient. Similarly, scores (0-4) and the maximum score for each PRO-CTCAE item will be recorded for each patient.

Radiographic Response Rate

A secondary endpoint of this study is (confirmed) radiographic response rate, defined as the proportion of patients in each arm whose best response is either complete response (CR) or partial response (PR) prior to crossover.

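### The adverse-event comparison has no time element, so for events that keep accruing it mixes toxicity with time on treatment; a common early window and time to first event should be added

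*Combined protocol and SAP*

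**What the plan says.** Section 13.5.3 of the combined protocol and SAP keeps the worst grade of each type of adverse event (AE) per patient and reviews frequency tables. It then states: "The overall adverse event rates will be compared between treatment groups using Chi-square test", with Fisher's exact test for sparse tables. For the patient-reported items, "PRO-CTCAE data will, at minimum, be analyzed similarly to CTCAE data". Section 13.3.2 sets the summary: "scores (0-4) and the maximum score for each PRO-CTCAE item will be recorded for each patient".

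The one named supplement is multiple imputation for missed PRO-CTCAE assessments. A closing sentence allows that "additional analyses of PRO-CTCAE data beyond those specified above may be undertaken"; it names no method and does not cover CTCAE. The only time limit is that AEs after crossover are left out, which can apply to placebo patients alone.

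On time under observation:

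- Section 7.1: "Treatment will continue until disease progression, unacceptable toxicity, or withdrawal of consent".
- Section 5.0, on collection: "Any adverse events that occur within 30 days of discontinuation of study treatment should be recorded in the last treatment cycle form". PRO-CTCAE booklets are given at the start of each cycle.
- Section 9.2 adds a late-event form for AEs of grade 2 or higher, at least possibly related, beyond 30 days. Section 13.5.3 does not say whether these enter its tables.
- Section 13.2 assumes placebo medians of 5 months (pancreatic) and 7 months (carcinoid). For cabozantinib it states "The PFS estimate corresponding to this HR is 8.8 months" (pancreatic) and "The PFS estimate for the cabozantinib corresponding to this HR is 12 months" (carcinoid).

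No section plans a fixed-window or time-to-event AE comparison, or a summary of treatment duration by arm.

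**The concern.** Time under AE observation is itself an outcome of treatment, because progression ends treatment. If cabozantinib delays progression, its patients have more months in which a first event can occur and more booklets in which a high score can be recorded. A difference in proportions may then reflect toxicity, longer observation, or both. If toxicity takes many patients off cabozantinib early, the same table can err the other way.

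Safety and tolerability versus placebo is a named secondary objective in each cohort (2.2.3 and 2.2.4), and this is its only specified between-arm test. Without treatment duration or any time-aware comparison, a reader cannot tell which case applies.

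**Working it through.** **1. Inputs.** From the documents:

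- medians as above, with arms of 124/61 and 141/69 (13.2);
- accrual of 31 and 35 months and minimum follow-up of 8 and 11 months (13.1);
- scans every 12 weeks (5.0).

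Assumed, because the documents give no figure:

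- the same AE hazard in both arms, 0.02-0.10 per month;
- a two-sided 0.05 level for the AE test, so 2.5% per direction;
- excess discontinuation on cabozantinib of 0 to 0.05 per month;
- progression found at the next scheduled scan;
- AEs counted only to 30 days after stopping.

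**2. The plan's own figures.** Events = (1.960 + 1.282)² / [p(1−p)(ln HR)²], where p is the cabozantinib share.

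- Pancreatic: 10.51 / (0.670 × 0.330 × 0.5653²) = 149.
- Carcinoid: 10.51 / (0.671 × 0.329 × 0.5390²) = 164.

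Both match Section 13.2, so the medians are read as the plan uses them.

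**3. Mechanism.** With constant AE hazard λ and treatment ending at rate μ = ln 2 / median, the proportion ever affected is λ/(λ+μ). At λ = 0.10 in both arms:

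- Pancreatic: 0.10/(0.10+0.0788) = 55.9% vs 0.10/(0.10+0.1386) = 41.9%, a gap of 14.0 points.
- Carcinoid: 0.10/(0.10+0.0578) = 63.4% vs 0.10/(0.10+0.0990) = 50.2%, a gap of 13.1 points (unrounded).

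Counting 30 further days reduces the gaps to 12.7 and 11.9 points. This simple form ignores the data cut, scan timing and toxicity stops.

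**4. Simulation with those features added** (2,000 to 20,000 trials per setting). Mean AE observation in months, cabozantinib vs placebo:

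| Excess discontinuation per month | Pancreatic | Carcinoid |
|---|---|---|
| 0 | 12.1 vs 8.9 | 15.2 vs 11.3 |
| 0.02 | 10.5 vs 8.9 | 12.7 vs 11.3 |
| 0.05 | 8.7 vs 8.9 | 10.1 vs 11.3 |

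Crude chi-square with no true difference in hazard, both cohorts, across the hazard range:

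| Hazard over time | Excess discontinuation per month | Cabozantinib falsely worse (nominal 2.5%) |
|---|---|---|
| Constant | 0 | 11-26% |
| Constant | 0.01 | 7-15% |
| Constant | 0.02 | 5-9% |
| Constant | 0.03 | 3-5% |
| Constant | 0.05 | 2% or less; falsely better in 3-9% |
| One quarter after month 3 | 0 | 4-11% |
| One quarter after month 3 | 0.01 | 3-7% |
| One quarter after month 3 | 0.02 | 2-5% |
| One quarter after month 3 | 0.03 | 2-3% |
| Months 0-3 only | 0 | 2-3% |

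For a severe PRO-CTCAE maximum (assumed 2-10% chance per booklet, within-patient correlation 0.3-0.8), the figure is 3-18%, or 2-5% with discontinuation of 0.02 per month.

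**5. Alternatives on the same assumptions.**

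- A three-cycle window gives 1-4% per direction.
- A log-rank test of time to first AE gives 1-4% when stopping is unrelated to AE risk. It gives up to 7% falsely better when AE-prone patients stop cabozantinib sooner.
- For very frequent AEs (0.5-1.0 per month), with treatment ending at the moment of progression, a 12-week window rejects in 7-13% (two-sided, nominal 5%), because some patients progress inside it.

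**The case against.** The strongest reply is that this is a preference, not an error. The chi-square is valid for what it measures, cumulative incidence as observed, and is adequate for early events. That stands.

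The reply on size also largely stands. Section 14.2.1 reports about fivefold accumulation by day 15. Section 1.2.2 reports that 81% of phase II NET patients completing at least one cycle needed a dose reduction. Section 8.2 allows no re-escalation and requires stopping for many toxicities. A hazard that falls over time, combined with some excess discontinuation, is therefore plausible, and together they bring the inflation close to nominal.

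Three further points stand in part:

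- Equal hazards is an artificial null for AEs already linked to the drug; Section 9.4 lists diarrhea, nausea, fatigue, hand-foot syndrome and hypertension at over 20%. A false rejection matters little there, but the size of the difference is still mixed with time.
- The 30-day limit is a collection rule, not a stated analysis period, and a late-event form exists. It is therefore listed as an assumption.
- Section 14.1.4 does plan models by assessment time, but for QLQ-C30 and GI.NET21 scores in an optional substudy, not for CTCAE or PRO-CTCAE.

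The reply that the plan already leaves room does not answer the point. The open sentence names no method and covers PRO-CTCAE only. Imputation addresses missed assessments, and the pharmacokinetic substudy concerns drug concentration. Choosing a window after seeing the data is what pre-specification avoids.

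**Conclusion.** The gap is real but modest. For AEs that keep accruing, the planned comparison mixes toxicity with time on treatment, provided cabozantinib prolongs PFS as designed and excess discontinuation does not offset this. On the stated assumptions, the false-worse rate is about 11-26% at most. It is about 5-15% with excess discontinuation of 0.01-0.02 per month, and about 2-7% if the hazard also falls to one quarter after month 3. It is about nominal (2-5%) at 0.03 per month. At 0.05 per month the error reverses, and cabozantinib looks falsely better in about 3-9%.

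A reader might infer that the AE test is invalid, or that it will make cabozantinib look falsely worse in a quarter of comparisons. The documents support neither. They give no AE hazards, no discontinuation rate and no level for this test, and the upper figure needs a constant hazard with no excess discontinuation. Neither direction nor size can be known in advance. The primary PFS test is unaffected.

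**What to change.** In Section 13.5.3:

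- Keep the crude tables and tests, labelled as cumulative incidence.
- Report treatment duration and AE observation time by arm, and state whether late-form events are counted.
- Pre-specify a supplementary between-arm comparison of worst CTCAE grade and worst PRO-CTCAE score within a common early window, such as the first three cycles.
- For CTCAE events, add time to first AE (log-rank or Cox, with cumulative incidence curves), at cycle resolution if onset dates are not collected; Section 9.1.1 has AEs entered by reporting period.
- Do not rely on a single person-time rate ratio. With equal hazards confined to months 0-3 it falls to 0.75-0.77 and understates cabozantinib toxicity.

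The cost is SAP wording and a few tables from data already collected by cycle. Three downsides should be stated. The window misses late events, which the crude tables and curves still show. It is not fully observed in patients who stop or progress inside it, so for very frequent AEs it can run modestly above nominal. For toxicity stops alone, with the 30-day tail counted, 12 weeks is 2.76 months and 2.76 − 0.99 = 1.77; exp(−0.02 × 1.77) = 97% and exp(−0.05 × 1.77) = 92% of cabozantinib patients are observed throughout. Last, time to first AE assumes that stopping is unrelated to AE risk, so it should be read beside the window result.

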13.5.4 Radiographic Response Rate

Radiographic response rate for both cohorts: the analyses for (confirmed) radiographic response rate will follow the ITT principle and will be conducted separately within each cohort (pancreatic NET and carcinoid tumor).

The proportion of patients with either (confirmed) CR or (confirmed) PR as their best response will be estimated using point estimates and 95% confidence intervals. For patients who elect to crossover to open-label cabozantinib at centrally-confirmed PD, only disease assessments prior to crossover will be considered for this endpoint. Any radiographic responses that occur after crossover will be analyzed separately in a descriptive fashion. Radiographic response rate will be compared between treatment arms using the 2-sample z-test to compare sample proportion at a one-sided 2.5% level of significance.

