2.2 Secondary Objectives

- **2.2.1** To determine whether cabozantinib can significantly improve overall survival (OS) compared to placebo in patients with advanced pancreatic NET whose disease has progressed after prior therapy.
- **2.2.2** To determine whether cabozantinib can significantly improve overall survival (OS) compared to placebo in patients with advanced carcinoid tumors whose disease has progressed after prior therapy.
- **2.2.3** To evaluate safety and tolerability of cabozantinib versus placebo in patients with advanced pancreatic NET using CTCAE and PRO-CTCAE.
- **2.2.4** To evaluate safety and tolerability of cabozantinib versus placebo in patients with advanced carcinoid tumors using CTCAE and PRO-CTCAE.
- 2.2.5 To evaluate the overall radiographic response rate of cabozantinib versus placebo in patients with advanced pancreatic NET whose disease has progressed after prior therapy.
- **2.2.6** To evaluate the overall radiographic response rate of cabozantinib versus placebo in patients with advanced carcinoid tumors whose disease has progressed after prior therapy.

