13.4 Stratification

The analysis will be done separately for the pancreatic NET and carcinoid tumor cohorts and will be stratified by the stratification factors listed in Section 4.6.

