13.5 Analysis Plan

13.5.1 Primary Endpoint

Treatment Efficacy Decision Rules

Interim analysis for both cohorts: Two interim analyses for futility only will be performed at the time at which 33% and 66% of the projected number of events have occurred. Gamma family spending function with parameter -6 will be used for futility boundary. The futility boundary will be considered non-binding. The specific critical p-values for declaring futility at each analysis are specified in the tables below. Specifically, at 2nd interim analysis in the pancreatic NET cohort: if p-value > 0.343, then the cabozantinib will be considered inefficacious. When progression-free survival (PFS) crosses futility boundary, the accrual will be suspended (if still ongoing), the enrolled patients will be followed per protocol, and the data will be reported.

Final analysis for both cohorts: The primary efficacy analysis will be performed at the time at which 100% of the projected number of events have occurred (149 PFS events for the pancreatic NET cohort, and 164 PFS events for the carcinoid tumor cohort). The specific critical p-values for declaring superiority or futility at each analysis are specified in the tables below. Specifically, at the final analysis for the pancreatic NET cohort: if the p-value ≤ 0.023 , then the cabozantinib will be deemed effective; if not, then the cabozantinib will be considered to have not met the criteria for efficacy. Per FDA instruction, the critical p-value of 0.023 is used for analysis, even though the statistical design has a Type I error of 0.025; therefore, we are spending 0.001 alpha for efficacy at each of the two interim analyses.

Pancreatic NET Cohort - Decision Boundary

Analysis time point (% events)	Number of events	Critical p- value for efficacy	HR for efficacy	Critical p- value for futility	HR for futility
33%	50	N/A	N/A	0.856	1.375
66%	99	N/A	N/A	0.343	0.917
100% (Final)	149	0.023*	0.711	0.023*	0.711

Carcinoid	Tumor	Cohort -	Decision	Boundary

Analysis time point (% events)	Number of events	Critical p- value for efficacy	HR for efficacy	Critical p- value for futility	HR for futility
33%	55	N/A	N/A	0.856	1.356
66%	109	N/A	N/A	0.343	0.921
100% (Final)	164	0.023*	0.723	0.023*	0.723

^{*} Alpha spending of 0.001 (for efficacy) per interim analysis (overall level = 0.025) is employed per FDA instruction.

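### Response rate has its own one-sided 2.5% test outside the PFS-then-OS hierarchy, with no nominal label, no stratification and no stated variance form

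*Combined protocol and SAP*

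**What the plan says.** Section 13.3.2 lists the secondary endpoints: "For both cohorts: overall survival, adverse events, and radiographic response rate". Section 13.5.4 gives the response test: "Radiographic response rate will be compared between treatment arms using the 2-sample z-test to compare sample proportion at a one-sided 2.5% level of significance". It sets no condition on PFS or OS. The only analysis it describes as descriptive is that of responses after crossover.

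Section 13.5.2 makes the multiplicity statement: "A hierarchical approach will be used to control for family-wise type-I error rate". Its one stated consequence is that "OS will be formally statistically tested only if the primary efficacy endpoint, PFS, is statistically significantly different between the two treatment groups". PFS and OS are each tested by a stratified log-rank test at one-sided 2.3%.

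Section 13.4, which refers to the factors in Section 4.6, says: "The analysis will be done separately for the pancreatic NET and carcinoid tumor cohorts and will be stratified by the stratification factors listed in" (the quote stops at the cross-reference). No endpoint is exempted. Section 4.6 defines four strata in each cohort, each with its own allocation schedule.

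If a futility boundary is crossed, Section 13.5.1 says that "the enrolled patients will be followed per protocol, and the data will be reported".

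The objectives differ in tone. For PFS and OS they ask whether cabozantinib significantly improves the endpoint. For response the aim is softer: "To evaluate the overall radiographic response rate of cabozantinib versus placebo in patients with advanced pancreatic NET", with a matching objective for carcinoid tumors.

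**The concern.** The plan claims family-wise error control but leaves one tested secondary efficacy endpoint outside it, with a separate 2.5%. Nothing says how a response p-value below that level may be described when PFS is not significant. A cohort that misses PFS, or stops for futility and reports its data, could therefore present response as statistically significant while following the plan exactly.

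Two details of the test add to this. The named z-test ignores the Section 4.6 factors, while Section 13.4 reads as a general rule and the PFS and OS tests follow it. The plan also does not say whether the z-test uses a pooled or an unpooled variance. When responses are rare and allocation is 2:1, that choice decides whether the test is conservative or well above its nominal level.

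**Working it through.** **Inputs from the plan.** PFS and OS are tested at one-sided 0.023 (13.5.1, 13.5.2) and response at one-sided 0.025 (13.5.4). Arms are 124 vs 61 (pancreatic) and 141 vs 69 (carcinoid) (13.2). Phase II response on cabozantinib was 3/20 and 6/41, both 15% (1.2.2). No placebo response rate, and no power for the response test, is given.

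**Assumptions.** Common null response rate 2–5%; for power, 15% vs 2%; full planned enrolment.

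**1. The plan's own alpha account.** 0.023 + 2 × 0.001 = 0.025, as 13.5.1 states. Response is not part of this account.

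**2. Bound with the ungated response test at its nominal level.**
- PFS or response, final analysis: 0.023 + 0.025 = 0.048. If independent: 1 − 0.977 × 0.975 = 0.0474.
- Counting the interim spend: 0.025 + 0.025 = 0.050.
- If PFS is truly effective, the pair at risk is OS and response, with the same bound 0.023 + 0.025 = 0.048.

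**3. Actual size of the z-test.** With x of n₁ and y of n₂ responders, z = (x/n₁ − y/n₂)/SE.
- Pooled: SE² = p̄(1 − p̄)(1/n₁ + 1/n₂), with p̄ = (x + y)/(n₁ + n₂).
- Unpooled: SE² = p₁(1 − p₁)/n₁ + p₂(1 − p₂)/n₂, with p₁ = x/n₁ and p₂ = y/n₂.

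Exact size is the summed binomial probability of all (x, y) with z ≥ 1.96:

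| Common rate | 124:61 pooled | 124:61 unpooled | 141:69 pooled | 141:69 unpooled |
|---|---|---|---|---|
| 2% | 0.0011 | 0.0695 | 0.0019 | 0.0782 |
| 3% | 0.0054 | 0.0837 | 0.0080 | 0.0821 |
| 4% | 0.0113 | 0.0743 | 0.0142 | 0.0696 |
| 5% | 0.0155 | 0.0640 | 0.0176 | 0.0607 |

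On a finer grid the unpooled maxima are 0.0839 (at 2.9%) and 0.0849 (at 2.55%).

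Adding 0.023 for PFS gives these bounds:
- Pooled: 2.4–3.8% (pancreatic) and 2.5–4.1% (carcinoid).
- Unpooled: 8.7–10.7% and 8.4–10.8%.

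**4. What the variance choice means in responders.** Take zero placebo responders in the pancreatic cohort.
- Unpooled: z = √(x/(1 − x/124)). At x = 3, z = 1.75; at x = 4, z = 2.03. The test rejects from 4 responders.
- Pooled: at x = 7, z = 0.0565/0.0298 = 1.89; at x = 8, z = 0.0645/0.0318 = 2.03. The test rejects from 8 responders.

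The same thresholds, 4 and 8, apply in the carcinoid cohort.

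**5. A stratified alternative.** One-sided CMH test without continuity correction, four strata with assumed shares 25/25/25/25% or 40/30/20/10%, 2:1 within strata, 200,000 replicates:
- Size at 2–5%: 0.1–1.6% (pancreatic) and 0.2–1.8% (carcinoid).
- Power at 15% vs 2%: about 87% and 92%. The pooled z-test gives 86.7% and 91.6% exactly.
- With assumed unequal strata (placebo 1/1/3/5%, cabozantinib 5/10/15/30%, 124:61): CMH 85.0%, pooled z 81.4%.

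**The case against.** The strongest reply is that Section 13.5.1 rests the efficacy verdict on PFS alone. Crossing the futility boundary, or missing 2.3% at the final analysis, settles that verdict against cabozantinib, and no response p-value can reverse it. Section 13.5.2 keeps the language of formal testing for OS, Section 13.5.4 speaks only of a comparison, and the objectives merely evaluate response. So response may well be meant as supportive, in which case the 4.8% bound describes a claim that nobody intends to make. This stands as a limit on the harm. It does not remove it, because Section 13.5.4 sets a significance level without saying that the result is supportive. The plan does give a caveat on type I error where it wants one, in the quality-of-life substudy (14.1.4).

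On stratification, Section 13.4 speaks of the analysis in the singular and may mean the primary one. The adverse-event comparisons in Section 13.5.3 are also unstratified, and an unstratified test is not invalid. At equal stratum rates the two tests perform alike. This part is therefore a matter of reconciling the sections, not of a wrong result.

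On variance, the pooled form is the natural one for a null of equal proportions, and with it the test is conservative. The 8.4–10.8% bound needs the unpooled form, a low common response rate and a confirmatory reading together. That is right, but the plan does not exclude the combination.

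**Conclusion.** The concern holds. Response rate carries a stated one-sided 2.5% test outside the declared hierarchy, with no PFS condition and no nominal label, and its relation to Section 13.4 is unresolved. The excess error concerns only what may be claimed for response. PFS keeps its level and so does OS gated on PFS.

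The bound across PFS and response is 4.8% per cohort at the nominal level. It is 2.4–4.1% with the pooled variance and 8.4–10.8% with the unpooled variance, over both cohorts, at assumed common response rates of 2–5%. The lack of a gate and label is a matter of text and is certain. The sizes depend on the assumed rates and on full enrolment. This should be corrected, but it does not threaten the primary conclusion.

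**What to change.** **Status of the test.** In Section 13.5.4, state that the response-rate p-value is nominal and supports no confirmatory claim, including after a futility stop. This is a wording change; the cost is giving up a stand-alone response claim.

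Alternatively, test response at one-sided 2.3% only after PFS is significant in that cohort, in a stated fixed order with OS. Gating on PFS alone, in parallel with OS at full level, is not enough (step 2 of the working). The order has a price:
- After OS, the response test waits for the final OS analysis, expected at "approximately 86 months and 68 months for the pancreatic NET and carcinoid tumor cohorts, respectively".
- Before OS, the OS test comes to depend on response, which changes the present hierarchy.

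**Method.** Replace the z-test by a one-sided CMH test stratified by the Section 4.6 factors. It uses a null variance, so it avoids the unpooled inflation and also agrees with Section 13.4. It has no material power cost at 2.5%. If gated at 2.3%, power at 15% vs 2% is about 86% (pancreatic) and 91% (carcinoid). An exact stratified version for sparse data is optional; if always used, power falls to about 82% and 88%.

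If the z-test is kept, specify the pooled variance in Section 13.5.4 and say in Section 13.4 that the response comparison is not stratified.
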